1.2.1 Randomization

Subjects who are normokalaemic (NK; $3.5 \le sK + \le 5.0 \text{ mmol/L}$) within 24 to 48 hours of enrolment in the open-label correction phase will be randomized 1:1 to either SZC 10g QD or placebo 10g QD. Randomization will be performed using randomly permuted blocks. The randomization codes will be computer generated and loaded into the IxRS database.

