1.3 Number of subjects

- Prior data: Proportion of patients with serum bicarbonate between 16-20 mmol/L inclusive who had a 3 mmol/L or greater increase in serum bicarbonate with SZC versus placebo from ZS-004,²⁰ Global Harmonize trial,²¹ and ZS-005.²²
- SZC: 92/235 = 0.39 achieved an increase in serum bicarbonate $\ge 3 \text{ mmol/L}$
- Placebo: 7/40 = 0.175 achieved an increase in serum bicarbonate $\ge 3 \text{ mmol/L}$
- Sample size estimate*
 - \circ 20% absolute difference:
 - Alpha=0.05, Power=80%
 - Control=0.175 with serum bicarbonate increase of 3mmol/L or more
 - SZC=0.39 with serum bicarbonate increase of 3mmol/L or more
 - *Actual effect size = 0.215
 - \circ N=68 per group (136)
 - N=148 (accounting for 8% drop-out from initial phase to randomized placebocontrolled phase)

*Sample size would be smaller if based on primary endpoint of mean sK+ (N=18 per arm).

Approximately 477 patients will be screened. Approximately 148 patients will be enrolled to the open-label phase of the study to achieve 136 randomly assigned to study intervention.

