3 PRIMARY AND SECONDARY VARIABLES

3.1 Time Points and Visit Windows

For all populations, assessments will be assigned to visits and analysis periods for categorical summaries as follows:

- Assessments with missing data and assessments marked "Not Done" will be considered as providing a missing response and are not permitted to be assigned to a visit window.
- The worst value (e.g. out of reference range preferred to within range; abnormal preferred to normal) will be used in each window. If multiple assessments fall within the same window with equal value, then the first non-missing will be used for the summary.

Scheduled day and visit window during the open-label period in Table 1 are with respect to the first dose of open-label study treatment. Baseline is defined as measurements taken at the screening visit on day 1 of the study.

Visit	Scheduled Day of Visit	Analysis Period	Protocol Visit Windows	Visit title in TFLs	Analysis Visit Windows
Visit 1	1	Screening/ Open-Label	Day 1	Visit 1 (Baseline)	Day 1
Visit 2	2	Open-Label	Day 2*	Visit 2	Day 2*
Visit 3	2 or 3	Randomized	Days 2 – 3*	Visit 3 (Randomization)	Days 2 – 3*
Visit 4	8	Randomized	Days 7 – 9	Visit 4	Days 4 – 11
Visit 5	15	Randomized	Days 14 – 16	Visit 5	Days 12 – 18
Visit 6	22	Randomized	Days 21 – 23	Visit 6	Days 19 – 25
Visit 7	29	Randomized	Days $28 - 30$	Visit 7 (EOT)	Days 26 – 32
Visit 8	36	Randomized	Days 33 – 39	Visit 8 (Follow-up)	Days 33 - 39

 Table 1 Definition of visit windows

* Assessments conducted on day 2 and day 3 will be assigned to visit 2 or 3 based on the nominally entered visit on the eCRF.

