4.2.7.1 Primary Efficacy Analysis

The primary efficacy endpoint is the occurrence (yes/no) of patients having normal sK+ (between 3.5 and 5.0 mmol/L inclusive) on Day 29 (Visit 7) without rescue treatment for hyperkalemia at any point during the randomized phase in the SZC versus placebo arm. Patients with missing sK+ will have these imputed as described in section 3.3.1. The number and percentage of subjects who achieved a response (Yes, No, Non-evaluable) will be summarized by randomized treatment group in the FAS.

The occurrence will be compared between treatment groups in the FAS using a logistic regression model (excluding non-evaluable responses) including response as the dependent variable and randomized treatment as an independent factor, it will be tested using a two-sided

alpha = 0.05. The common odds ratio will be derived together with the two-sided 95% confidence interval.

Documentation will be provided to check the underlying assumptions for the logistic regression model. Standardized residuals will be presented in a scatter plot by alphanumerical subject ID. Subjects with standardized residuals > 3.0 will be listed. Influential observations on the regression coefficients will be detected by calculating Cook's D statistic (In SAS applied with proc reg with the plots=cooksd option) and presented in a diagnostic plot by alphanumerical subject ID. Subjects with Cook's D statistic > 4/sqrt(n) will be listed.

Estimand Attributes

In line with ICH E9 (R1) addendum, 5 attributes (treatment, population, endpoint, intercurrent events, and population-level summary) have been specified to translate the primary and key secondary efficacy objectives into treatment effects that are to be estimated (estimands).

Endpoint:

• Hyperkalaemia response, defined as an observed sK+ within 3.5-5.0 mEq/L at Day 29 (Visit 7)

Population:

• All subjects who achieve normokalemia at the end of the open-label correction phase, and are randomized

Treatment:

• SZC or Placebo. Patients with $sK+ \ge 6.0 \text{ mmol/L}$ will be managed with rescue therapy employing local standard of care.

Intercurrent Event Strategy:

- Discontinuation of treatment (Treatment policy strategy, i.e. regardless of the intercurrent event)
- Use of rescue therapy for hyperkalaemia at any point during the randomized placebocontrolled period (Composite variable strategy, i.e. considered to be non-response).

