4.2.7.3 Secondary Efficacy Analyses

1 Mean change in serum bicarbonate from baseline (Day 1) to Day 29 (Visit 7) in SZC versus placebo arm.

Serum bicarbonate will be summarized and listed in the FAS using the visits of Baseline (Visit 1), randomization (Visit 3) and Day 29 (Visit 7). Patients with missing serum bicarbonate values at visit 7 will have these imputed with serum bicarbonate values from visit 6 if available, as described in section 3.3.2. The mean change in serum bicarbonate from baseline (Day 1) will be analyzed using analysis of covariance (ANCOVA) analyses at the significance level 5% (2-sided), with randomized treatment as main effect and baseline bicarbonate as covariate. For patients needing rescue treatment for low bicarbonate, the last value of the POCT bicarbonate during the randomized period prior to rescue treatment will be analyzed. The analysis will be based on the FAS.

Documentation will be provided on the underlying assumptions for the ANCOVA model. This will include a check that the residuals are approximately normally distributed by plotting a histogram of the residuals for the model as well as a Shapiro-Wilk test which will reject the null hypothesis that the residuals are normally distributed if p<0.05. Secondly, the homogeneity of variance will be visually checked through an inspection of a plot of residuals versus predicted values from the model. Finally, the homogeneity of slopes will be determined by conducting an ANCOVA analysis where the dependent variable is Day 29 (Visit 7) serum bicarbonate and the independent variables are randomized treatment group, baseline serum bicarbonate. If p>0.05 for the interaction term, then we will accept the homogeneity of the treatment slopes.

Estimand Attributes

Endpoint:

• Change in serum bicarbonate at Day 29 (Visit 7) from baseline

Population:

• All subjects who achieve normokalemia at the end of the open-label correction phase, meet inclusion/exclusion criteria and are randomized

Treatment:

• SZC or Placebo. Patients with $sK+ \ge 6.0 \text{ mmol/L}$ will be managed with rescue therapy employing local standard of care.

- Discontinuation of treatment (Treatment policy strategy, i.e. regardless of the intercurrent event)
- Use of rescue therapy for hyperkalaemia at any point during the placebo-controlled period (Treatment policy strategy, i.e. regardless of the intercurrent event).

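### The bicarbonate ANCOVA (secondary endpoint #1) adjusts only for the range-restricted Day 1 value and leaves out the Visit 3 value taken at randomization, which gives up some precision

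*SAP*

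**What the plan says.** SAP Section 3.1 fixes the reference point for change: "Baseline is defined as measurements taken at the screening visit on day 1 of the study". Section 4 agrees in general terms, taking the last observation before the first open-label dose. Under Section 1.2, patients enter the open-label phase with POCT bicarbonate of 16-20 mmol/L. They then take open-label SZC for up to 48 hours and are randomized once potassium is 3.5-5.0 mmol/L. Section 1.2.1 describes the allocation: "Randomization will be performed using randomly permuted blocks". No stratification factor is named.

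For endpoint #1, Section 4.2.7.3 summarises and lists bicarbonate "using the visits of Baseline (Visit 1), randomization (Visit 3) and Day 29 (Visit 7"). The ANCOVA that follows is fitted "with randomized treatment as main effect and baseline bicarbonate as covariate", and baseline there means Day 1. Neither of the two sensitivity analyses listed for this endpoint in Section 4.2.7.4 uses Visit 3, and both are cancelled because of early termination.

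The primary model in Section 4.2.7.1 is a logistic regression "including response as the dependent variable and randomized treatment as an independent factor", with no covariate.

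**The concern.** Randomization happens at Visit 3, after an active run-in, but the only covariate in the ANCOVA dates from before the run-in. It was also the entry criterion. Selecting patients on a narrow band of a variable shrinks its spread and weakens its correlation with the outcome, so Day 1 bicarbonate explains less of the Day 29 variation than an unrestricted measurement would. Visit 3 bicarbonate is closer in time to Day 29, has no entry band on it, and is already summarised.

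Leaving it out has two consequences. Predictable between-patient variation stays in the residual, so the interval is wider than it needs to be. And if the arms differ by chance at Visit 3, the model does not correct for it. Endpoint #1 is the first secondary test in the hierarchy of Section 4.2.7, so its precision affects whether later endpoints are formally tested.

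**Working it through.** **The plan's own figure.** Section 1.3 gives 68 per group for the responder endpoint of a rise of at least 3 mmol/L: "Control=0.175 with serum bicarbonate increase of 3mmol/L or more", SZC 0.39, alpha 0.05 (two-sided), power 80%. With pooled variance and mean proportion 0.2825:

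n = [1.960 × √(2 × 0.2825 × 0.7175) + 0.842 × √(0.175 × 0.825 + 0.39 × 0.61)]² / 0.215² = (1.248 + 0.520)² / 0.0462 = 67.6, so 68 per group and 136 in total. Then 136 / 0.92 = 147.8, so 148 enrolled.

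The figures reproduce. They use no covariate and do not depend on this point.

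**Inputs for the covariate question.** From the SAP: entry band 16-20 mmol/L, 1:1 allocation, Day 1 baseline, Visit 3 available. Assumed, because the SAP gives no SD or correlation: mean bicarbonate 20, stable between-patient SD 1.5-2.5, visit-to-visit SD 1.0-2.0, values rounded to whole mmol/L. Sizes of 10 and 20 per arm are illustrations; the SAP does not state the final number after early termination.

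**Step 1: effect of the entry band.** Selecting on 16-20 cuts the Day 1 SD to 1.2-1.3, while the Visit 3 SD is 1.7-2.4. In a separate check (unrestricted SD 2-4, mean 18), a Day 1 to Day 29 correlation of 0.5-0.7 falls to about 0.20-0.52 after selection.

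**Step 2: residual variance.** With Day 1 bicarbonate as covariate, analysing the Day 29 value or the change from Day 1 gives the same treatment contrast and the same residual. So the quantity needed is the residual variance of Day 29 given Day 1 and Visit 3, divided by that given Day 1 alone:

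| Between-patient SD | Visit-to-visit SD | Ratio |
|---|---|---|
| 1.5 | 1.5 | 0.89 |
| 2.0 | 1.5 | 0.85 |
| 2.5 | 1.5 | 0.82 |
| 2.0 | 1.0 | 0.81 |
| 1.5 | 2.0 | 0.93 |

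The reduction is 7-19%.

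**Step 3: small samples.** Estimating one more covariate inflates the variance of the treatment estimate. With N patients in total, going from one to two covariates multiplies it by about (N − 4)/(N − 5).
- 20 per arm: 36/35 = 1.029, so 0.81-0.93 becomes about 0.83-0.96.
- 10 per arm: 16/15 = 1.067, so 0.81-0.93 becomes about 0.86-0.99.

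Simulation of the treatment estimate agrees to within its error: a reduction of about 5-18% at 20 per arm and about 0-14% at 10 per arm. On the 95% confidence interval (four of the five SD pairs), the half-width shrinks by 3-10% at 68 per arm, by 2-9% at 20 per arm, and by between nil and 7% at 10 per arm.

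**Step 4: chance imbalance.** The difference between arms at Visit 3, in SD units, has SD √(2/n). The chance that it exceeds 0.3 SD is 50% at 10 per arm, 34% at 20 and 8% at 68. Only part of this reaches the treatment difference. A variance reduction of 7-19% implies a partial correlation of √0.07 = 0.26 to √0.19 = 0.44, so an imbalance of 0.3 SD (given Day 1) moves the contrast by 0.3 × 0.26 = 0.08 to 0.3 × 0.44 = 0.13 residual SD. The standard error at 20 per arm is about √(2/20) = 0.32 residual SD.

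**Step 5: the primary endpoint.** In an illustrative logistic simulation with assumed correlations of 0.3, 0.5 and 0.7 between Visit 3 and Day 29 sK+, adjustment moved power from about 51% to 53%, 59% and 69% at 68 per arm. At 18 per arm it moved from about 48% to 45%, 48% and 53%, so the direction of the effect depends on the sample size.

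**The case against.** The strongest reply is that nothing here is wrong. ANCOVA of change from Day 1 with the Day 1 value as covariate is a standard, valid analysis and matches the endpoint in Section 1.1. Randomization protects the contrast. Regression to the mean and any run-in shift common to both arms cancel, and the reported standard error already allows for chance imbalance. The gain rests on assumed SDs and shrinks as the trial shrinks: at 10 per arm, adding Visit 3 widened the interval in 30-61% of simulated trials, depending on the SD pair. The sponsor also cut covariates deliberately because of early termination (Amendment History; Section 4.2.7.2). All of this stands, and it limits the point to efficiency. It does not remove the point, because the average gain at 20 per arm is real under every SD pair tried, and one continuous covariate is a much smaller demand than the eight-factor list that was cut.

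A reader might infer more than the SAP supports:
- **That the run-in resets bicarbonate.** The SAP documents only that potassium is normal at randomization. The case for Visit 3 does not need a bicarbonate shift, since it is the last value before randomized treatment either way.
- **That imbalance at Visit 3 passes straight into the treatment difference.** It passes only through the partial slope (Step 4).
- **That early termination makes the omission more costly.** Large imbalances become more likely, but the precision gained by adjusting becomes smaller.
- **That the primary model has the same defect and should include Visit 3 sK+.** Section 4.2.7.1 sets the summary as the odds ratio of the proportion of responders, which is a marginal contrast; adding a continuous covariate makes it conditional. Visit 3 potassium is itself restricted to 3.5-5.0 mmol/L, and power at 18 per arm changes by only about −4 to +6 points. That trade-off does not justify changing the primary model.

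**Conclusion.** The point holds for endpoint #1 as a matter of precision. The model relies on a range-restricted value from before the run-in and leaves out a later one that is already summarised. The loss is moderate: about 7-19% of residual variance in large samples, about 5-18% of the variance of the treatment estimate at 20 per arm, and about 0-14% at 10 per arm. These figures assume the SDs listed above and no difference between patients in run-in response. If such differences exist and persist to Day 29, the gain would be larger; if they fade before Day 29, it would be smaller. There is no bias and no inflation of type I error, and the primary analysis is not affected.

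**What to change.** In Section 4.2.7.3, endpoint #1, before unblinding:
- Keep change from Day 1 to Day 29 as the outcome and Day 1 bicarbonate as covariate.
- Add Visit 3 POCT bicarbonate as a second continuous covariate. State that the value used is the one taken before the first randomized dose. The SAP does not give the timing of the sample relative to dosing, and Table 1 places Visit 3 in the randomized period.
- State a simple fill-in for a missing Visit 3 value that uses neither treatment arm nor Day 29 data, such as the mean of the observed Visit 3 values over both arms.

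Leave the primary treatment-only logistic model unchanged. Adjustment for Visit 3 sK+ is at most an optional sensitivity analysis, labelled as a conditional odds ratio.

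The cost is a few lines of SAP text, one degree of freedom and no new data. If the final sample is very small, there may be little or no gain.

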1.2 Study design

This is a prospective, randomized, double-blind, placebo-controlled, parallel, multicenter, Phase IIIb study to investigate the safety and efficacy of SZC in patients with hyperkalemia and low bicarbonate (or metabolic acidosis).

The study will be conducted in the United States (US) at approximately 35 investigative sites.

This study consists of a short screening visit (Day 1), an open-label correction period (up to 48 hours), a 4-week randomized treatment period, and a follow-up period (7 days after the last administration of study medication). The total study treatment duration, consisting of open-label and randomized periods, will be 29 days.

Screening will be performed using potassium and bicarbonate value from a study-approved point-of-care test (POCT) to determine eligibility of consenting patients to enter the openlabel correction phase. Patients who meet the POCT eligibility criteria of serum potassium (sK+) between 5.1-5.9 mmol/L inclusive, AND serum bicarbonate between 16-20 mmol/L inclusive, will be enrolled into the open-label correction phase. All baseline parameters should be measured/collected prior to administration of the first dose of study drug in the open-label initial phase.

In the open-label initial phase, patients will receive open-label SZC orally at a dose of 10 g three times daily (TID) for up to 48 hours, depending on POCT potassium value.

Patients who achieve normokalemia (K+ between 3.5 and 5.0 mmol/L inclusive) within 24-48 hours will be randomized 1:1 into the double-blind randomized treatment phase to receive 10 g SZC or placebo once daily (QD) starting dose for the following 28 days. Patients who achieve normokalemia after 24 hours will be randomized and will not need to continue on 10 g SZC TID for another 24 hours.

Study treatment will end with the Day 29 visit, which will be followed by the end of study visit 7 days after the last administration of study medication.

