- Use of rescue therapy for low bicarbonate at any point during the randomized controlled period (While on treatment strategy, e.g. last observation carried forward).
- Death prior to Day 29 (Visit 7) (While on treatment strategy, e.g. last observation carried forward).
- POCT bicarbonate measurement unavailable for Visits 6 and 7 (Hypothetical strategy, assume response is missing).
- Subject lost to follow-up prior to Day 29 (Visit 7) (Hypothetical strategy, assume response is missing).

- Least squares mean estimate in the SZC treatment group compared to the placebo group.
- 2 Occurrence (yes/no) of patients having an increase in serum bicarbonate of ≥2 mmol/L on Day 29 (Visit 7) from baseline without need for rescue treatment for low bicarbonate in SZC versus placebo arm.

For secondary efficacy endpoints #2 - #7 the number and percentage of subjects with the endpoint (Yes, No, Non-evaluable) will be summarized by randomized treatment group in the FAS. Patients with missing sK+ or serum bicarbonate values at visit 7 will have these imputed as described in sections 3.3.1 and 3.3.1. The occurrence of each secondary efficacy endpoint will be compared between treatment groups in the FAS using a logistic regression model including the binary response endpoint as the dependent variable and randomized treatment as an independent factor, it will be formally tested using a two-sided alpha = 0.05 if the hierarchical testing strategy supports conducting a formal hypothesis test. The common odds ratio will be derived together with the two-sided 95% confidence interval.

For each secondary efficacy endpoint #2 - #7, documentation will be provided to check the underlying assumptions for the logistic regression model. Standardized residuals will be presented in a scatter plot by alphanumerical subject ID. Subjects with standardized residuals > 3.0 will be listed.

Endpoint:

• Serum bicarbonate response, defined as an increase from baseline in serum bicarbonate value ≥2 mmol/L at Day 29 (Visit 7)

Population:

• All subjects who achieve normokalemia at the end of the open-label correction phase, meet inclusion/exclusion criteria and are randomized

Treatment:

• SZC or Placebo. Patients with $sK+ \ge 6.0 \text{ mmol/L}$ will be managed with rescue therapy employing local standard of care.

- Discontinuation of treatment (Treatment policy strategy, i.e. regardless of the intercurrent event)

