- 4 Occurrence (yes/no) of patients having a normal sK+ (between 3.5 and 5.0 mmol/L inclusive) on Day 29 (Visit 7) and an increase in serum bicarbonate of ≥3 mmol/L on Day 29 (Visit 7) from baseline without need for rescue treatment for hyperkalemia or low bicarbonate.

Endpoint:

• Hyperkalaemia response, defined as an observed sK+ within 3.5-5.0 mEq/L at Day 29 (Visit 7) and serum bicarbonate response, defined as an increase in serum bicarbonate value of ≥3 mmol/L at Day 29 (Visit 7) from baseline.

Population:

• All subjects who achieve normokalemia at the end of the open-label correction phase, meet inclusion/exclusion criteria and are randomized

Treatment:

• SZC or Placebo. Patients with $sK+ \ge 6.0 \text{ mmol/L}$ will be managed with rescue therapy employing local standard of care.

- Discontinuation of treatment (Treatment policy strategy, i.e. regardless of the intercurrent event)
- Use of rescue therapy for hyperkalaemia at any point during the placebo-controlled period (While on treatment strategy, e.g. last observation carried forward).
- Use of rescue therapy for low bicarbonate at any point during the randomized controlled period (While on treatment strategy, e.g. last observation carried forward).
- Death prior to Day 29 (Visit 7) (Composite variable strategy, i.e. considered to be non-response).
- Subject lost to follow-up prior to Day 29 (Visit 7) (Hypothetical strategy, i.e. assume response is not evaluable).
- Subject with no sK+ or POCT K measurement at visit 6 or visit 7 (Hypothetical strategy, i.e. assume response is not evaluable).
- Subject with no POCT or central laboratory bicarbonate measurements at visit 6 or visit 7 (Hypothetical strategy, i.e. assume response is not evaluable).

- Odds ratio of the proportion of responders in the SZC treatment group compared to the placebo group.
- 5 Occurrence (yes/no) of patients having serum bicarbonate ≥22 mmol/L on Day 29 (Visit 7) without need for rescue treatment for low bicarbonate in SZC versus placebo group

Endpoint:

• Serum bicarbonate response, defined as a serum bicarbonate value of ≥22 mmol/L at Day 29 (Visit 7)

Population:

• All subjects who achieve normokalemia at the end of the open-label correction phase, meet inclusion/exclusion criteria and are randomized

Treatment:

• SZC or Placebo. Patients with $sK+ \ge 6.0 \text{ mmol/L}$ will be managed with rescue therapy employing local standard of care.

Intercurrent Event Strategy:

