4.2.7.4 Secondary Efficacy Analysis – Sensitivity Analyses

Two sensitivity analyses will be conducted for secondary efficacy endpoint #1:

- (i) Analysis as described for secondary endpoint #1 using PPS
- (ii) Analysis as described above but with full imputation of bicarbonate using central laboratory measurements, as described in section 3.3.2, is conducted before the response is assumed to be missing. In addition, the ANCOVA model will include a binary variable to indicate if the dependent variable is central laboratory measurement.

Two sensitivity analyses will be conducted for each of the secondary efficacy endpoints #2-#7.

- Principal secondary analysis as described where the logistic regression model will include: race, gender, age at baseline (<65, ≥65), CKD stage at baseline (3, 4), diabetes status at baseline (Yes, No), POCT bicarbonate level at entry (16-18, 19-20), POCT type (i-Stat, Piccolo) and baseline use of RAASi therapy (Yes, No) as independent factors.
- Principal secondary analysis as described but conducted in the PPS.

Due to the early termination of the trial, the sensitivity analyses described above will not be conducted due to an insufficient sample size.

Statistical Analysis Plan D9480C00022 - External 4.0

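### The logistic models for the bicarbonate responder endpoints #2-#6 leave out baseline bicarbonate, which costs some efficiency and leaves chance baseline imbalance uncorrected, although the test remains valid

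*SAP*

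**What the plan says.** - **Endpoints #2-#7 (SAP 4.2.7.3).** The arms are compared "using a logistic regression model including the binary response endpoint as the dependent variable and randomized treatment as an independent factor". Treatment is the only term.
- **Endpoint #1 (same section).** Mean change in bicarbonate is analysed by ANCOVA "with randomized treatment as main effect and baseline bicarbonate as covariate".
- **Endpoint #5.** The response is "Occurrence (yes/no) of patients having serum bicarbonate ≥22 mmol/L on Day 29 (Visit 7) without need for rescue treatment for low bicarbonate". Endpoint #6 adds normal sK+ to this. Endpoints #2-#4 are built on a rise from baseline of at least 2 or 3 mmol/L.
- **Planned adjustment (4.2.7.4).** A sensitivity model for #2-#7 listed eight covariates, among them "POCT bicarbonate level at entry (16-18, 19-20), POCT type (i-Stat, Piccolo) and baseline use of RAASi therapy (Yes, No) as independent factors". The section closes by stating that "the sensitivity analyses described above will not be conducted due to an insufficient sample size". Section 6 repeats the cancellation.
- **Randomisation (1.2.1).** "Randomization will be performed using randomly permuted blocks". The SAP names no stratification factor.
- **Entry range (1.2).** Patients with "serum bicarbonate between 16-20 mmol/L inclusive, will be enrolled into the open-label correction phase".

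**The concern.** Baseline bicarbonate bears on every one of these endpoints. For the 22 mmol/L target, a patient entering at 20 needs a rise of 2 and a patient entering at 16 needs a rise of 6. For #2-#4 the baseline value is part of the response definition. The value is an entry criterion, so it should exist for every eligible patient, and the SAP already treats it as relevant in #1 and in the cancelled models.

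Two things are at stake. The first is power: endpoint #3 sized the trial at 80%, and under the fixed order in 4.2.7 a failure at #2 or #3 makes every later p-value descriptive. The second is chance imbalance. In a trial stopped early, the arms can differ at baseline by more than they would at full size, and an unadjusted responder comparison passes that difference on.

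**Working it through.** **1. The plan's own figure.** Inputs from SAP 1.3: 0.175 and 0.39, alpha 0.05 (taken as two-sided, as for the tests in 4.2.7.3), power 80%. The pooled proportion is (0.175 + 0.39)/2 = 0.2825.

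n = [1.960·√(2·0.2825·0.7175) + 0.842·√(0.175·0.825 + 0.39·0.61)]² / 0.215² = 67.6, so 68 per arm.

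Power at 68 per arm is 80.2%, and 136/0.92 = 147.8 gives 148 enrolled. All the stated figures reproduce, using an unadjusted two-proportion test.

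**2. Assumptions for the effect of adjustment (none is in the SAP).** Baseline is uniform on the integers 16-20. Residual SD is 2.5 mmol/L. The slope of Day-29 on baseline bicarbonate runs from 0 to 1. Arm means are set so that the responder rates are 0.175 and 0.39, and the same rates are used for #5. Each setting has 3,000 trials at 68 per arm, with a Wald test of treatment, with and without continuous baseline.

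| Slope | #3 power, unadjusted → adjusted | #5 power, unadjusted → adjusted |
|---|---|---|
| 0 | 80.6% → 86.3% | 79.9% → 79.9% |
| 0.25 | 79.0% → 83.3% | 79.2% → 80.0% |
| 0.5 | 78.9% → 81.1% | 80.0% → 81.8% |
| 0.75 | 79.7% → 80.5% | 80.6% → 83.4% |
| 1 | 78.7% → 79.0% | 79.4% → 85.2% |

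The standard error of one power figure is √(0.8·0.2/3000) = 0.7 points, so the smallest differences are not distinguishable from zero. The pattern has a simple cause. At slope 1, baseline carries no information on the change; at slope 0, it carries none on the Day-29 level. With arm means set from the ≥3 rates, endpoint #2 behaves like #3 and also gains about 0 to 6 points. Endpoints #4 and #6, which also require normal sK+, were not simulated.

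**3. Type I error in the same runs.** Unadjusted 0.036-0.049; adjusted 0.040-0.052.

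**4. Precision on the risk-difference scale.** The variance of the unadjusted estimate divided by that of the baseline-standardised one, at 68 per arm, is 1.00-1.16 for #3 and 1.00-1.18 for #5. At worst, the unadjusted analysis needs about 16-18% more patients for the same precision.

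**5. Chance imbalance.** The variance of a uniform baseline on 16-20 is 2, so the SD of the difference in arm means is √(2·2/n). This is 0.24 mmol/L at 68 per arm and 0.45 at 20 per arm. The 20 is only an illustration, because the SAP does not give the number randomised. A difference of 0.5 mmol/L is thus about 2 SD at full size and about 1 SD at 20 per arm. Its effect on the risk difference at 68 per arm is:

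| Slope | #3 unadjusted | #5 unadjusted |
|---|---|---|
| 0 | -0.059 | -0.001 |
| 0.5 | -0.034 | +0.032 |
| 1 | +0.003 | +0.062 |

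The largest shift is 0.062/0.215 = 29% of the planned effect. After adjustment every shift is 0.006 or less in size. At intermediate slopes #3 and #5 move in opposite directions, so an imbalance could make the two results appear to disagree.

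**6. Power at the illustrative 20 per arm.** The change is about -1 to +4 points for ≥3 and ≥22, and up to about +7 for ≥2. Power stays low either way: with SD 2.75 and slope 0.4-1.0 it is 28% for ≥3 in both models, 11-14% against 12-16% for ≥22, and 32-33% against 33-36% for ≥2.

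**The case against.** The best defence is that nothing here is wrong in the strict sense. The arms are randomised, the unadjusted comparison is valid, and it matches both the sample-size calculation in 1.3 and the summary measure in 4.2.7.3, an odds ratio of responder proportions that reads as marginal. A covariate makes the model odds ratio conditional (about 3.1 becomes 3.8 for #3 at slope 0), which changes the target unless it is dealt with. The gain is modest, rests on quantities that the SAP does not give, and may be near zero for one type of endpoint. At 20 per arm, adjustment can even cost a little: the variance ratio falls as low as 0.975 where baseline is uninformative. Bicarbonate change is already adjusted in #1, which is tested earlier, and the wider adjustment was dropped for a stated reason.

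Most of this stands, and it limits the point to efficiency and conditional accuracy. Two parts do not carry. A small sample is a reason to drop eight covariates but a weak reason to drop this one: 4.2.7.2 keeps a logistic model with a single covariate (POCT type) for the primary endpoint after early termination. And the shift in target can be removed by standardising over baseline.

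A reader might also infer that type I error is inflated, or that #1 and #2-#6 contradict each other. Neither follows. The error rate holds, and different models for different endpoints are a choice.

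**Conclusion.** The point holds as a recommended improvement. As the SAP stands, #2-#6 are not adjusted for baseline bicarbonate by model, and the SAP names no stratification that would do it by design.

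At 68 per arm the cost is about 0 to 6 points of power. It is largest for #5 when the slope is near 1, largest for #2 and #3 when it is near 0, and close to nothing at the opposite extreme. At the number actually randomised, the power gain is small, and the stronger reason is imbalance: up to about 0.06 on the risk difference for a 0.5 mmol/L baseline gap. For scale, the SD of the unadjusted risk difference at 20 per arm is about 0.14, so this is a correction well inside sampling error.

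It is tempting to call baseline a strong predictor throughout, or to expect adjustment to rescue a truncated trial. The first depends on an unknown slope. The second is not borne out by the low power in either model. All sizes rest on the assumed baseline distribution, SD and slope, and #4 and #6 are covered by reasoning only.

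**What to change.** Before unblinding, amend 4.2.7.3 as follows:

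- Add Day-1 POCT bicarbonate as a single continuous covariate to the logistic models for #2-#6. The continuous form matches #1 and avoids the 16-18/19-20 split of the cancelled model.
- From that model, report the baseline-standardised (marginal) odds ratio with its confidence interval as the estimate, and a standardised risk difference if wanted, so that the result still answers the stated summary measure.
- State that Firth penalisation will be used if responders are sparse.
- Keep the treatment-only result as supportive.

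No new data are needed. The cost is a short SAP amendment and slightly more analysis work, chiefly the standardisation and its interval. The raw model odds ratio becomes conditional on baseline and should be labelled so wherever it is shown.
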